10.2.4 Investigational Product Compliance

Review subject compliance with the IP usage and adjunct product usage and collect all used and unused study IPs and other products that were dispensed.

10.2.5 Adverse Event Collection: Safety Assessment

Assess and record any adverse events that are observed or reported since the previous visit, including those associated with changes in concomitant medication dosing.

10.2.6 Slit Lamp Biomicroscopy: Safety Assessment

SLE of the cornea, iris/anterior chamber and lens must be performed in both eyes before instillation of any diagnostic eye drops.

10.2.7 Device Deficiencies: Safety Assessment

Assess and record any Device Deficiencies that are reported or observed since the previous visit. Requirements for reporting device deficiencies in the study can be found in Section 11.

10.3 Unscheduled Visits

If a subject visit occurs between any regularly scheduled visit and the visit is conducted by study personnel, this visit must be documented as an Unscheduled Visit. If the subject seeks medical attention outside the clinic (for example, at an Emergency Room) or at the clinic but is seen by nonstudy personnel, the investigator is to capture adverse event-related information on the Adverse Event form upon becoming aware.

During all unscheduled visits, the investigator must conduct the following procedures:

- Collect Adverse Event information, as applicable
- Collect device deficiency information, as applicable
- Record changes in medical condition or concomitant medication
- Perform Slit Lamp Biomicroscopy exam

The investigator may perform additional procedures for proper diagnosis and treatment of the subject. The investigator must document this information in the subject's case history source documents.

If during an Unscheduled Visit the subject is discontinuing the IP or discontinuing from the study, the investigator must conduct Exit procedures according to Table 3–1 Schedule of Study Procedures and Assessments and Section 10.4.3, as possible. Do not complete an Unscheduled Visit if a subject is exiting between scheduled study visits. An Early Exit Visit should be completed instead.

Unplanned Lens Replacement is to be used only in the event of a device deficiency or if a lens is lost or damaged, so as to maintain lens wear until the follow-up visit.

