9.3 Treatment Assignment / Randomization

Subjects will be randomized in a 1:1 ratio to receive treatment in crossover sequence test product then comparator product or comparator product then test product, respectively.

Sequence	EDC/randomization integration system	Lens Name
Sequence 1	LID210464/AOHG MF	MF/AOHG MF
Sequence 2	AOHG MF/LID210464	AOHG MF/

[figure not shown]
Only after signing the ICF, a subject will be assigned a subject number by the electronic data capture system.

[figure not shown]
A randomization list will be generated using a validated system that automates the random assignment of treatment arms to randomization numbers in the specified ratio. Subjects will be assigned treatment according to the randomization list uploaded in the randomization system. The randomization list will be generated and maintained by the study sponsor.

At Visit 1, all eligible subjects will be randomized via the EDC/randomization integration system to one of the treatments (lens sequences). The investigator's delegate will access the respective system after confirming that the subject meets all the eligibility criteria. A randomization number will be automatically assigned to the subject according to the subject randomization list but will not be communicated to the site user. The EDC/randomization integration system will inform the site user of the treatment (lens sequence) assignment to be dispensed to the subject. The same randomization assignment will be followed for lens fitting.

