9.4 Treatment Masking

This study is double-masked, with subjects randomized to use MF or AOHG MF contact lenses for the duration of the 30 day treatment period.

This level of masking will be maintained throughout the conduct of the study. Unmasking will occur only after all planned study data have been validated, and the database locked.

Masked study personnel must avoid seeking information that may compromise masking.

In the event of a medical emergency where the knowledge of subject treatment is required, an individual investigator will have the ability to unmask the treatment assignment for a specific subject after contacting an appropriate study sponsor representative if time allows.

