10.4.2 Discontinuations

Discontinued subjects are individuals who voluntarily withdraw or are withdrawn from the study by the investigator after signing informed consent and after randomization.

Subject numbers of discontinued subjects must not be re-used (i.e., subject replacement is not allowed).

Subjects may discontinue from study or study treatment at any time for any reason. Subjects may also be discontinued from study treatment at any time if, in the opinion of the investigator, continued treatment poses a risk to their health.

If a subject discontinues from study treatment, every effort must be made to keep the subject in the study and to continue with the study assessments as specified in the schedule of study procedures and assessments until the final visit.

For subjects discontinuing from the study, the investigator must complete all Exit procedures according to Table 3–1 Schedule of Study Procedures and Assessments and Section 10.4.3, if the subject is willing and able, and if in the opinion of the investigator it is safe for the subject to do so.

The investigator must document the reason for study or treatment discontinuation in the subject's case history source documents.

To ensure the safety of all subjects who discontinue early, investigators must assess each subject and, if necessary, advise them of any therapies and/or medical procedures that may be needed to maintain their health.

10.4.3 Schedule of Procedures and Assessments for Subjects Discontinued from Investigational Product

Other than screen failures, if a subject discontinues from the study, the subject should undergo an Early Exit Visit, as possible. Refer to Table 3–1.

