12.1 Subject Evaluability

Final subject evaluability must be determined prior to breaking the code for masked treatment (lens sequence) assignment and locking the database, based upon the Deviations and Evaluability Plan.

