1.3 Randomization

A member of the Randomization Programming group at Alcon who is not part of the study team will generate the randomized allocation schedule(s) for study lens sequence assignment. Randomization will be implemented in the Electronic Data Capture (EDC)/randomization integration system.

Qualifying subjects will be randomized in a 1:1 ratio to receive treatment (lens) in crossover sequence [REDACTED]

Sequence	EDC/randomization integration system	Lens Name
Sequence 1	LID210464/AOHG MF	██████ MF/AOHG MF
Sequence 2	AOHG MF/LID210464	AOHG MF/██████ MF

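### Do Protocol 10.3, 10.4.2 and 10.4.3 leave it open in a way that matters whether a subject who stops the Period 1 lens goes on to Lens 2?

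*Protocol*

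**What the plan says.** - **Protocol 10.3** covers a subject seen at an Unscheduled Visit: if "the subject is discontinuing the IP or discontinuing from the study, the investigator must conduct Exit procedures", as far as possible, under Table 3-1 and 10.4.3. It adds that a subject who is exiting between scheduled visits has an Early Exit Visit in place of an Unscheduled Visit.
- **Protocol 10.4.3** is headed "Schedule of Procedures and Assessments for Subjects Discontinued from Investigational Product". Its one rule is that, screen failures apart, "if a subject discontinues from the study, the subject should undergo an Early Exit Visit, as possible". It then refers back to Table 3-1.
- **Protocol 10.4.2** says: "If a subject discontinues from study treatment, every effort must be made to keep the subject in the study", with the scheduled assessments continued to the final visit. It assigns Exit procedures to subjects who leave the study.
- **Protocol Table 3-1** has an Early Exit column, and dispenses Lens 2 at Visit 3 with no condition about Lens 1.
- The word *treatment* is used in two ways. Protocol 12.1 speaks of final evaluability "prior to breaking the code for masked treatment (lens sequence) assignment", and Protocol 9.3 glosses the word in the same way. Protocol 9.4 refers to wearing the "contact lenses for the duration of the 30 day treatment period", and SAP 1.3 has subjects "randomized in a 1:1 ratio to receive treatment (lens) in crossover sequence".

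**The concern.** A site that follows 10.3 for a subject who stops only the product is sent to a section whose heading fits and whose rule does not. Section 10.4.2 asks for retention, which looks like the opposite of exit. If *study treatment* in 10.4.2 meant the whole lens sequence, a Period 1 stopper would have stopped both lenses. If it meant one lens, the Visit 3 dispensing of Lens 2 would still stand.

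Two sites could therefore handle the same subject differently. One route gives two scheduled Lens 2 distance VA values (Visit 3 dispense and Visit 4), about 30 days of exposure and a place in the Lens 2 safety denominator. The other gives none of these. Subjects are not replaced, and the SAP does not impute the primary endpoint.

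**Working it through.** **Reading the passages together.** 10.3 governs the day of the stop, and 10.4.2 governs what happens afterwards. The Early Exit column of Table 3-1 contains history, concomitant medications, VA, biomicroscopy, adverse events, device deficiencies and the Exit Form. Apart from the Exit Form, these are assessments that can be done at the stop without ending follow-up. Because 10.3 cites Table 3-1 directly and 10.4.3 only refers back to it, the site has an operative instruction despite the heading. The sentence on Early Exit Visits concerns subjects who are exiting. No passage states this joint reading, but none rules it out.

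**The word *treatment*.** None of the four places that show its two senses uses the term found in 10.4.2, *study treatment*. Protocol 9.3, Protocol 12.1 and SAP 1.3 gloss the word on the spot, in statements about randomization or the masked code. Elsewhere *study treatment* appears in the heading of Protocol 11.5, whose text is about the identity of the assigned device. Section 9 of the Protocol, on treatments administered, opens with the investigational products. One definition would not settle dispensing in any case, because 10.4.2 does not mention it.

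**Is the analysis defined on both routes?** Yes. The FAS is all randomized subjects exposed to a study lens. The mixed model uses whatever VA values exist, without imputation. Safety is classified by the lens actually worn (Protocol 12.2.1, SAP 2.1), and each adverse event counts under the exposed lens until the next lens starts (SAP 5.3.1).

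**The plan's own figure.** Inputs from SAP 7: SD of the paired difference 0.0845, margin 0.05, one-sided alpha 0.05, power 90%.

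Total n = (0.0845 × (1.645 + 1.282) / 0.05)² = 24.46, or 12.23 per sequence, rounded up to 13. By the noncentral t with n − 2 degrees of freedom, 24 subjects give 87.8% power and 26 give 90.07%. The stated 13 per sequence reproduces. On the same basis 84 subjects give 99.99% and 72 give 99.96%.

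**Effect of the two routes on precision.** The variance of the Day 30 lens difference is c′(Σ Xᵢ′Vᵢ⁻¹Xᵢ)⁻¹c. Here Xᵢ holds lens, visit, lens by visit, period and sequence (habitual lens stratum omitted), with four VA values per subject, and c picks the lens effect at Day 30. Within-subject variance is 0.0845²/2 = 0.00357. Assumed ranges are a between-period correlation of 0.3 to 0.7 and a period-level share of within-subject variance of 0 to 0.6. Of 84 subjects, k stop in Period 1 with only the Day 1 Lens 1 value, all in Sequence 1. The values of k are assumptions.

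With k = 0 the SE is 0.0845/√84 = 0.00922 and the upper limit at an observed difference of zero is 1.66 × 0.00922 = 0.0153.

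| k | SE without Lens 2 | SE with Lens 2 | Increase | Upper limit without | Upper limit with |
|---|---|---|---|---|---|
| 1 | 0.00927–0.00928 | 0.00924–0.00926 | 0.2–0.4% | 0.0154 | 0.0153–0.0154 |
| 4 | 0.00943–0.00945 | 0.00930–0.00937 | 0.9–1.5% | 0.0156–0.0157 | 0.0154–0.0156 |
| 8 | 0.00967–0.00972 | 0.00938–0.00954 | 1.9–3.4% | 0.0160–0.0161 | 0.0156–0.0158 |

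The largest gap between routes is about 0.0005 logMAR, or 0.0005/0.05 = 1% of the margin. Since 84 is the planned number of completers out of about 96 enrolled, stoppers may come on top of 84. The SE then does not exceed 0.00922 on either route.

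**The case for a change.** The strongest argument the other way is that exit and retention are opposite instructions for one subject, and that an SE comparison measures precision only. Three points support it.

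- **Bias.** Stoppers may see worse with the lens they stop. If their VA on that lens counted and was 0.2 logMAR worse (assumed), 6 of 96 would move the difference by 6/96 × 0.2 = 0.0125 and 12 of 96 by 0.025, which is 25% to 50% of the margin. This is a fair worry about who stops, but it concerns the value on the stopped lens. Neither route supplies a Day 30 value there, and the visible text does not make an Early Exit value a Day 30 value. Dispensing Lens 2 does not alter that.
- **Movement of the estimate.** A simulation with 6 or 12 stoppers showed the estimate moving by about 0.001 between exit and Lens 2. With 300 runs and an SE near 0.009, the simulation error of each mean is 0.009/√300 = 0.0005, so a gap of that size is compatible with noise.
- **Near VA.** Near VA drives the 42 per sequence in the Protocol Summary. At the largest SD compatible with that number (about 0.155, back-calculated), power falls from 90.0% with 84 subjects to 88.7% with 80. A Period 1 stopper lacks one of the two Day 30 values on either route, so that subject is not a complete pair in any case.

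The textual part stands: the heading and body of 10.4.3 name different groups, no passage joins 10.3 to 10.4.2, and Lens 2 dispensing to a retained stopper is not addressed. Where a site meets such a subject, the sponsor must reconcile these passages. This review takes no view on which clinical rule is right.

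**Conclusion.** No change to the plan follows. The 10.4.3 heading is a clerical slip. The exit and retention passages can be read in sequence, and the differing uses of *treatment* are explained where they occur. What remains is a missing operational detail that the Manual of Procedures may already supply; the Protocol makes that manual part of the clinical investigation plan and places detailed procedures there. The SAP yields a defined analysis whichever way a site acts.

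For up to 8 stoppers among 84, the choice changes the SE by at most about 3.4% and the upper limit by about 0.0005 logMAR, with the limit no higher than 0.0161 against 0.05. This rests on the SAP's SD of 0.0845, an observed difference of zero, and assumed stopper counts, correlations and variance shares. It addresses precision and does not rule out that stoppers differ from other subjects. That question is the same on both routes. Confidence is moderate, because the Manual of Procedures, the Deviations and Evaluability Plan and the text of Protocol 12.5 were not available.

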10.4 Discontinued Subjects

10.4.1 Screen Failures

Subjects who were excluded from the study after signing the informed consent and prior to randomization to product/dispense of study product.

The investigator must document the reason for screen failure in the subject's case history source documents.

Subject numbers must not be re-used.

10.4.2 Discontinuations

Discontinued subjects are individuals who voluntarily withdraw or are withdrawn from the study by the investigator after signing informed consent and after randomization.

Subject numbers of discontinued subjects must not be re-used (i.e., subject replacement is not allowed).

Subjects may discontinue from study or study treatment at any time for any reason. Subjects may also be discontinued from study treatment at any time if, in the opinion of the investigator, continued treatment poses a risk to their health.

If a subject discontinues from study treatment, every effort must be made to keep the subject in the study and to continue with the study assessments as specified in the schedule of study procedures and assessments until the final visit.

For subjects discontinuing from the study, the investigator must complete all Exit procedures according to Table 3–1 Schedule of Study Procedures and Assessments and Section 10.4.3, if the subject is willing and able, and if in the opinion of the investigator it is safe for the subject to do so.

The investigator must document the reason for study or treatment discontinuation in the subject's case history source documents.

To ensure the safety of all subjects who discontinue early, investigators must assess each subject and, if necessary, advise them of any therapies and/or medical procedures that may be needed to maintain their health.

10.4.3 Schedule of Procedures and Assessments for Subjects Discontinued from Investigational Product

Other than screen failures, if a subject discontinues from the study, the subject should undergo an Early Exit Visit, as possible. Refer to Table 3–1.

10.5 Clinical Study Termination

The study sponsor reserves the right to suspend or close the investigational site or suspend or terminate the study in its entirety at any time.

If the clinical study is prematurely terminated or suspended by the study sponsor:

- The study sponsor must:
 - Immediately notify the investigator(s) and subsequently provide instructions for study termination.
 - Inform the investigator and the regulatory authorities of the termination/suspension and the reason(s) for the termination/suspension.
- The investigator must:
 - Promptly notify the IRB/IEC of the termination or suspension and of the reasons.
 - Provide subjects with recommendations for poststudy treatment options as needed.

The investigator may terminate the site's participation in the study for reasonable cause.

Breaking of the masked treatment codes will be done after locking the database.

10.5.1 Follow-Up of Subjects After Study Participation Has Ended

Following this study, the subject will return to their eye care professional for their routine eye care.

11 ADVERSE EVENTS AND DEVICE DEFICIENCIES

11.1 General Information

An AE is any untoward medical occurrence, unintended disease or injury, or untoward clinical signs (including abnormal laboratory findings) in subjects, users, or other persons,

whether or not related to the investigational medical device (test product). Refer to the Glossary of Terms and figures below for categories of AEs and SAEs.

Figure 11-1 Categorization of All Adverse Events

[figure not shown]
[figure not shown]

Figure 11-2 Categorization of All Serious Adverse Events

Specific Events Relevant to this Protocol

Serious Adverse Events

In addition to reporting all AEs (serious and nonserious) meeting the definitions, the Investigator must report any occurrence of the following as an SAE:

- An ocular infection including a presumed infectious ulcer with any of the following characteristics:
 - Central or paracentral location
 - o Penetration of Bowman's membrane
 - o Infiltrates > 2 mm diameter
 - o Iritis
 - Increase in intraocular pressure
 - Culture positive for microorganisms
 - Increasing size or severity at subsequent visits
- Any central or paracentral corneal event (such as neovascularization) that results in permanent opacification
- Hypopyon
- Hyphema
- Neovascularization within the central 6 mm of the cornea
- Permanent vision loss as defined by loss of 2 or more lines of BCVA at distance (e.g., with manifest refraction or habitual correction) from enrollment visit that fails to resolve
- Uveitis (anterior, intermediate, or posterior)
- Corneal abrasion affecting ≥50% of corneal surface area

Significant Non-Serious Adverse Events

A significant non-serious AE is a device-related, non-sight threatening adverse event that warrants discontinuation of any contact lens wear for greater than or equal to 2 weeks. In addition, the Investigator must report any occurrence of the following as a Significant Non-Serious Adverse Event:

- Peripheral non-progressive non-infectious ulcers
- All symptomatic corneal infiltrative events

- Corneal staining score greater than or equal to grade 3 (Refer to MOP for grading scales)
- Temporary vision loss as defined by loss of 2 or more lines of BCVA at distance (e.g., with manifest refraction or habitual correction) from enrollment visit that persists for 2 or more weeks
- Neovascularization score greater than or equal to grade 2 (Refer to MOP for grading scales)

The above events are based on the categories provided in the ISO 11980 and the US FDA Premarket Notification (510(k)) Guidance Document for Daily Wear Contact Lenses.

Device Deficiencies

A device deficiency is inadequacy of a medical device with respect to its identity, quality, durability, reliability, safety, or performance. A device deficiency may or may not be associated with patient harm (i.e., ADE or SADE); however, not all ADEs or SADEs are due to a device deficiency. The Investigator should determine the applicable category listed in the Device Deficiency eCRF for the identified or suspect device deficiency and report any patient harm separately. Examples of device deficiencies include the following:

- Failure to meet product specifications (e.g., incorrect lens power/diameter/base curve/color)
- Lens/solution cloudy
- Lens surface/edge defect
- Torn lens during handling/in pack
- Packaging deficit (e.g., mislabeled product, tampered seal, leaking bottle/container)
- Suspect product contamination

11.2 Monitoring for Adverse Events

At each visit, after the subject has had the opportunity to spontaneously mention any problems, the Investigator should inquire about AEs by asking the standard questions shown below and report as applicable:

- "Have you had any health problems since your last study visit?"
- "Have there been any changes in the medicines you take because of a new health issue since your last study visit?"

In addition, changes in *any protocol-specific parameters and/or questionnaire (e.g., biomicroscopy findings, subjective ratings questionnaires)* evaluated during the study are to be reviewed by the Investigator. Any untoward (unfavorable and unintended) change in *a protocol-specific parameter or questionnaire response* that is clinically relevant, in the opinion of the Investigator, is to be reported as an AE. These clinically relevant changes will be reported regardless of causality.

11.3 Procedures for Recording and Reporting

AEs are collected from the time of informed consent Any pre-existing medical conditions or signs/symptoms present in a subject prior to the start of the study (i.e., before informed consent is signed) are not considered AEs in the study and should be recorded in the Medical History section of the eCRF.

In addition, temporary lens awareness or visual changes during the fitting process are not considered AEs if the Investigator assesses that the symptom(s) can reasonably resolve within the anticipated adaptation period.

For each recorded event, the ADEs and SAEs documentation must include: date of occurrence, severity, treatment (if applicable), outcome, and assessments of the seriousness and causality. In addition, the Investigator must document all device deficiencies reported or observed with test and comparator products on the Device Deficiency eCRF. The site must submit all available information on ADEs, SAEs, and device deficiencies to the study sponsor immediately as follows:

- ADEs or SAEs are documented on the *Serious Adverse Event and Adverse Device Effect* eCRF within 24 hours of the Investigator's or site's awareness.
- Device deficiencies are documented on the *Device Deficiency* eCRF within 24 hours of the Investigator's or site's awareness.
- Additional relevant information after initial reporting must be entered into the eCRF as soon as the data become available.
- Document any changes to concomitant medications on the appropriate eCRFs.
- Document all relevant information from Discharge Summary, Autopsy Report, Certificate of Death etc., if applicable, in narrative section of the *Serious Adverse Event and Adverse Device Effect* eCRF.

Note: Should the EDC system become non-operational, the site must complete the appropriate paper *Serious Adverse Event and Adverse Device Effect* and/or *Device*

Deficiency Form. The completed form is emailed to the study sponsor at [contact] according to the timelines outlined above; however, the reported information must be entered into the EDC system once it becomes operational.

Any AEs and device deficiencies for non-study marketed devices/products (i.e., CLEAR CARE Cleaning & Disinfecting Solution, will be considered and processed as spontaneous (following the post-market vigilance procedures) and should be communicated to the device's/product's manufacturer as per local requirements.

Study sponsor representatives may be contacted for any protocol related question and their contact information is provided in the Manual of Procedures that accompanies this protocol.

Further, depending upon the nature of the AE or device deficiency being reported, the study sponsor may request copies of applicable portions of the subject's medical records. The Investigator must also report all AEs and device deficiencies that could have led to a SADE according to the requirements of regulatory authorities or IRB/IEC.

Intensity and Causality Assessments

Where appropriate, the Investigator must assess the intensity (severity) of the AE based on medical judgment with consideration of any subjective symptom(s), as defined below:

Intensity (Severity)

Mild An AE is mild if the subject is aware of but can easily tolerate the sign

or symptom.

Moderate An AE is moderate if the sign or symptom results in discomfort

significant enough to cause interference with the subject's usual

activities.

Severe An AE is severe if the sign or symptom is incapacitating and results in

the subject's inability to work or engage in their usual activities.

For every AE in the study, the Investigator must assess the causality (Related or Not Related to the medical device or study procedure). An assessment of causality will also be performed by study sponsor utilizing the same definitions, as shown below:

Causality

Related An AE classified as related may be either definitely related or possibly

related where a direct cause and effect relationship with the medical device or study procedure has not been demonstrated, but there is a reasonable possibility that the AE was caused by the medical device or

study procedure.

Not Related An AE classified as not related may either be definitely unrelated or

simply unlikely to be related (i.e., there are other more likely causes

for the AE).

The study sponsor will assess the AEs and may upgrade the Investigator's assessment of seriousness and/or causality. The study sponsor will notify the Investigator of any AEs that is upgraded from non-serious to serious or from unrelated to related.

